##### 6.1.1.2. Joint Distribution of Pure Virologic Failure and Study Drug Discontinuation

PVF at Week 48 is defined similarly as PVF at Week 12, except that the time point is at Week 48. For subjects with PVF at Week 48, event time is defined as the day of the first occurrence of confirmed HIV-1 RNA  $\geq$  50 copies/mL or the collection time of last available HIV-1 RNA  $\geq$  50 copies/mL followed by premature discontinuation of study.

Drug discontinuation (DC) is defined as subjects who prematurely discontinued study drug on or prior to the upper limit of the Week 48 analysis window. The premature study drug discontinuation date is the last dose date defined in Section 3.7.1.

To better understand the relationship between study drug discontinuation and pure virologic failure by Week 48, subjects will be classified into the following 4 categories:

- **Success** is defined as subjects who were pure virologic responders and did not discontinue study drug prematurely.
- **PVF alone** is defined as subjects who were pure virologic failures but did not discontinue study drug prematurely.

- **DC alone** is defined as subjects who were pure virologic responders but discontinued study drug prematurely.
- **PVF and DC** is defined as subjects who were pure virologic failures and discontinued study drug prematurely.

For ‘DC alone’ and ‘PVF and DC’ categories, reasons for DC will be grouped into 3 mutually exclusively categories: (1) **DC due to drug**, including discontinuation due to lack of efficacy, death, or AE; (2) **DC due to choice**, including discontinuation due to noncompliance, withdrew consent, protocol violation, or investigator’s discretion (3) **DC due to administration**, including lost to follow-up or pregnancy. For each premature study drug discontinuation group under ‘PVF and DC’ category, outcomes will further be broken down into 3 mutually exclusively categories based on the sequence when PVF and DC occurred: (1) **PVF-DC** is defined as subjects who met the criteria for PVF followed by DC; (2) **PVF/DC** is defined as subjects who met the criteria for PVF and DC at the same time; (3) **DC-PVF** is defined as subjects who had DC first and then met the criteria for PVF.

The pure virologic response analysis will be descriptive in nature using the FAS only. No inferential statistics will be provided.

#### 6.1.1.3. Time to Pure Virologic Failure Analysis

For subjects who do not experience a confirmed rebound (ie, HIV-1 RNA  $\geq$  50 copies/mL on 2 consecutive visits or the last available HIV-1 RNA  $\geq$  50 copies/mL followed by premature discontinuation of study) by the data cut, subjects will be censored at the last HIV-1 RNA collection date. For subjects who experience confirmed rebound, the time to PVF will be defined as the earlier time of 2 consecutive HIV-1 RNA  $\geq$  50 copies/mL or the last available HIV-1 RNA  $\geq$  50 copies/mL followed by premature discontinuation of study.

Time to PVF will be analyzed using the Kaplan-Meier method by treatment group using the FAS. The log rank test will be performed to compare the difference in time to PVF between the 2 treatment groups stratified by the prior treatment regimen (ie, STB, ATR, or ATV/boosted+TVD).

Lastly, subjects who failed according to snapshot algorithm, pure virologic failure analysis algorithms, or had premature study drug discontinuation by Week 48 will be listed.

#### 6.1.2. Statistical Hypothesis for the Primary Efficacy Endpoint

No formal statistical hypotheses are being tested.

#### 6.1.3. Primary Analysis of the Primary Efficacy Endpoint

The number and proportion of subjects with PVR and PVF at Week 12 will be summarized overall and by Parts 1 and 2. Two-sided 95% CIs will be constructed for the overall estimate of PVR and PVF using the normal approximation and the exact method.

#### **6.1.4. Secondary Analysis for the Primary Efficacy Endpoint**

##### **6.1.4.1. Analysis of Pure Virologic Response at Week 12**

Subjects who took Stribild or Descovy as part of the baseline ARV regimen were excluded from the FAS. A sensitivity analysis will be performed by including these subjects in the PVR analysis.

#### **6.1.5. Subgroup Analysis for the Primary Efficacy Endpoint**

No subgroup analyses will be performed.

### **6.2. Secondary Efficacy Endpoints**

#### **6.2.1. Definition of Secondary Efficacy Endpoints**

Secondary efficacy endpoints are:

- HIV-1 RNA < 50 copies/mL at Weeks 24 and 48 using PVR (See Section 6.2.2.2)
- HIV-1 RNA < 50 copies/mL at Weeks 12, 24 and 48 using the Food and Drug Administration (FDA) snapshot analysis (sensitivity analysis)
- The proportion of subjects with HIV-1 RNA < 20 copies/mL at Weeks 12, 24, and 48 as determined by the US FDA-defined snapshot algorithm.
- The proportion of subjects with HIV-1 RNA < 50 copies/mL at Weeks 12, 24, and 48 as defined by 2 different missing data imputation methods.
- The change from baseline in CD4+ cell count at Weeks 12, 24, and 48
- The change from baseline in CD4% at Weeks 12, 24, and 48

#### **6.2.2. Analysis Methods for Secondary Efficacy Endpoints**

##### **6.2.2.1. Analysis of Pure Virologic Response at Weeks 24 and 48**

The number and proportion of subjects with PVR at Weeks 24 and 48 will be summarized overall and by Parts 1 and 2. Two-sided 95% CIs will be constructed for the overall estimate of PVR using the normal approximation and the exact method.

##### **6.2.2.2. Time to Pure Virologic Failure Analysis**

For subjects who do not experience a confirmed rebound (ie, HIV-1 RNA  $\geq$  50 copies/mL on 2 consecutive visits or the last available HIV-1 RNA  $\geq$  50 copies/mL followed by premature discontinuation of study), subjects will be censored at the last HIV-1 RNA collection date. For subjects who experience confirmed rebound, the time to PVF will be defined as the earlier time of 2 consecutive HIV-1 RNA  $\geq$  50 copies/mL or the last available HIV-1 RNA  $\geq$  50 copies/mL followed by premature discontinuation of study.

Time to PVF will be analyzed using the KM method by Part 1 and Part 2 using the FAS.

Lastly, subjects who failed according to snapshot algorithm, pure virologic failure analysis algorithms, or had premature study drug discontinuation by Week 48 will be listed.

6.2.2.3. Analysis of proportion of subjects with HIV-1 RNA < 50 copies/mL at Weeks 12, 24, and 48 as determined by the US FDA-defined snapshot algorithm

The analysis windows for Weeks 12, 24, and 48 are defined in [Table 3-1](#). All HIV-1 RNA data collected on-treatment (eg, data collected up to 1 day after the last dose date of study drug) will be used in the US FDA-defined snapshot algorithm. Virologic outcome will be defined as the following categories:

- **HIV-1 RNA < 50 copies/mL:** this includes subjects who have the last available on-treatment HIV-1 RNA < 50 copies/mL in the analysis window
- **HIV-1 RNA ≥ 50 copies/mL:** this includes subjects:
  - a. Who have the last available on-treatment HIV-1 RNA ≥ 50 copies/mL in the analysis window, or
  - b. Who do not have on-treatment HIV-1 RNA data in the analysis window and
    - 1) Who discontinue study drug prior to or in the analysis window due to lack of efficacy (note: Lack of efficacy is defined as having the check-box for Lack of efficacy marked on the Study Drug Completion eCRF), or
    - 2) Who discontinue study drug prior to or in the analysis window due to AE or death and have the last available on-treatment HIV-1 RNA ≥ 50 copies/mL
    - 3) Who discontinue study drug prior to or in the analysis window due to reasons other than AE, death, or lack of efficacy and have the last available on-treatment HIV-1 RNA ≥ 50 copies/mL
- **No Virologic Data (in the Window):** this includes subjects who do not have on-treatment HIV-1 RNA data in the analysis window because of the following:
  - 1) Discontinuation of study drug prior to or in the analysis window due to AE or death and the last available on-treatment HIV-1 RNA < 50 copies/mL, or
  - 2) Discontinuation of study drug prior to or in the analysis window due to reasons other than AE, death, or lack of efficacy and the last available on-treatment HIV-1 RNA < 50 copies/mL, or
  - 3) Missing data during the window but on study drug.

Virologic outcomes for the US FDA-defined snapshot algorithm will also be listed.

*Note:* For switch study populations, the US FDA-defined snapshot algorithm classifies subjects who discontinue study drug due to AE or death and have the last available on-treatment HIV-1 RNA value  $\geq 50$  copies/mL as HIV-1 RNA value  $\geq 50$  copies/mL. For a treatment naïve study population, the US FDA-defined snapshot algorithm classifies these subjects as having No Virologic Data in the analysis window.

The number and percentage of subjects achieving HIV-1 RNA  $< 50$  copies/mL, HIV-1 RNA  $\geq 50$  copies/mL, and reasons for no virologic data at Weeks 12, 24, and 48 will be summarized overall and by Parts 1 and 2. Two-sided 95% CIs will be constructed for overall estimates using the exact method.

6.2.2.4. Analysis of proportion of subjects with HIV-1 RNA  $< 20$  copies/mL at Weeks 12, 24, and 48 as determined by the US FDA-defined snapshot algorithm

The number and percentage of subjects achieving HIV-1 RNA  $< 20$  copies/mL, HIV-1 RNA  $\geq 20$  copies/mL, and reasons for no virologic data at Weeks 12, 24, and 48 will be summarized overall and by Parts 1 and 2. Two-sided 95% CIs will be constructed for the overall estimate of the proportion of subjects with HIV-1 RNA  $< 20$  copies/mL using the exact method.

6.2.2.5. Analysis of Proportion of Subjects with HIV-1 RNA  $< 50$  copies/mL  
(Missing Excluded and Missing Failure Approaches)

The proportion of subjects with HIV-1 RNA  $< 50$  copies/mL will also be analyzed using the following 2 methods for imputing missing HIV-1 RNA values, where the proportions will be expressed as percentages in all tables, listings, and figures:

- Missing Failure (M F)

In this approach, all missing data will be treated as HIV-1 RNA  $\geq 50$  copies/mL. The denominator for percentages at a visit is based on the number of subjects in the FAS.

- Missing Excluded (M E)

In this approach, all missing data will be excluded in the computation of the proportions (ie, missing data points will be excluded from both the numerator and denominator). The denominator for percentages at a visit is based on the number of subjects in the FAS with non-missing HIV-1 RNA value at that visit.

For both M F and M E analyses, the number and percentage of subjects with HIV-1 RNA in the following categories will be summarized:

- $< 50$  copies/mL
- $< 20$  copies/mL
  - $< 20$  copies/mL Not Detectable
  - $< 20$  copies/mL Detectable

- 20 to < 50 copies/mL
- $\geq 50$  copies/mL
- Missing (only applicable for M F analysis)

The proportion of subjects with HIV-1 RNA < 50 copies/mL as defined by the 2 different missing data imputation methods will be summarized for each visit. Two-sided 95% CIs will be constructed using the exact method.

For M F analysis, results will be summarized and plotted for visits up to and including Week 12. For M E analysis, results will be summarized for each visit.

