 - CD4+ cell count change from Day 1 at Weeks 12, 24 and 48
-

Statistical Methods:

The primary endpoint of pure virologic response (PVR) with HIV-1 RNA < 50 copies/mL at Week 12 will be computed.

The following criteria are considered for classifying subjects as a pure virologic responder at Week 12:

- Subject remains on study treatment
- No confirmed virologic rebound as defined by:
 - HIV-1 RNA \geq 50 copies/mL on 2 consecutive visits
 - HIV-1 RNA \geq 50 copies/mL during study followed by premature discontinuation

Note: For confirmation of viral rebound, the first HIV-1 RNA must occur on or before the upper limit of the Week 12 analysis window, the confirming event (i.e., the second of the consecutive HIV-1 RNAs or premature study discontinuation) can occur after the upper limit of the Week 12 analysis window.

Subjects who meet the above criteria are pure virologic responders at Week 12; otherwise subjects are pure virologic failures (PVF) at Week 12.

Similar definition would hold for PVR at Weeks 24 and 48.

Sensitivity analyses of virologic failure will use the FDA snapshot analysis (and other sensitivity analyses such as missing equal failure) at Weeks 12, 24 and 48.

An interim efficacy analysis will be conducted when the first 50 subjects complete 12 weeks of treatment. Based on the analysis of the primary efficacy variable (HIV-1 RNA < 50 copies/mL) using pure virologic response, study conduct may be altered based on the recommendations of the internal monitoring committee.

Descriptive statistics will summarize baseline characteristics, efficacy, and safety endpoints.

The primary analysis will describe the point estimate and 95% confidence interval around the proportion of subjects with HIV-1 RNA < 50 copies/mL for the primary endpoint. If the observed pure virologic response rate is 90%, then with 100 participants, the width of the 95% CI will be \pm 5.9% (large sample size approximation and binomial distribution).

This study will be conducted in accordance with the guidelines of Good Clinical Practice (GCP) including archiving of essential documents.

GLOSSARY OF ABBREVIATIONS AND DEFINITION OF TERMS

°C	degrees Celsius
°F	degrees Fahrenheit
3TC	lamivudine
ABC	abacavir
AE	adverse event
AIDS	Acquired Immune Deficiency Syndrome
AhR	aryl hydrocarbon receptor
AK	adenylate kinase
ALT	alanine aminotransferase
ANC	absolute neutrophil counts
ANOVA	analysis of variance
ARV	antiretroviral
AST	aspartate aminotransferase

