### 6.3. Changes From Protocol-Specified Efficacy Analyses

For the primary efficacy endpoint, PVR at Week 12, the protocol specifies that 95% CIs will be generated using the normal approximation method, but in the SAP, both the normal approximation and the exact methods are specified.

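### SAP 6.2.2.5 limits the Missing = Failure analysis to Week 12, against its own preceding sentence, the SAP 6.2.1 endpoint and the protocol synopsis, and SAP 6.3 does not declare it

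*SAP*

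**What the plan says.** SAP 6.2.2.5 defines two ways of handling a missing HIV-1 RNA value. M=F counts it as 50 copies/mL or more and divides by the whole Full Analysis Set (FAS). M=E drops it from both numerator and denominator.

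On which visits are reported, the documents say:

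- **SAP 6.2.2.5, general sentence:** the proportion "as defined by the 2 different missing data imputation methods will be summarized for each visit", with exact 95% confidence intervals.
- **SAP 6.2.2.5, on M=F:** "results will be summarized and plotted for visits up to and including Week 12".
- **SAP 6.2.2.5, on M=E:** "For M E analysis, results will be summarized for each visit".
- **SAP 6.2.2.5, table rows:** "Missing (only applicable for M F analysis"), so the row counting missing subjects exists only in the M=F table.
- **SAP 6.2.1, secondary endpoint:** the proportion below 50 copies/mL "at Weeks 12, 24, and 48 as defined by 2 different missing data imputation methods".
- **Protocol synopsis, Statistical Methods:** snapshot "and other sensitivity analyses such as missing equal failure) at Weeks 12, 24 and 48".
- **SAP 6.3:** the only declared change from the protocol's efficacy analyses is that for Week 12 pure virologic response (PVR) "both the normal approximation and the exact methods are specified".

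**The concern.** SAP 6.2.2.5 gives two instructions that cannot both be followed, and the narrower one conflicts with the SAP's own endpoint list and with the protocol synopsis. The restriction is one-sided: it removes the method that penalises missing data and keeps the method that ignores it.

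Durability at Weeks 24 and 48 is a stated secondary objective. Its main measure, PVR, does not penalise dropout as the SAP defines it. The only criterion in SAP 6.1.1.1 is absence of confirmed rebound, and SAP 6.1.1.2 has a category for responders who stopped study drug. M=F beside M=E is the like-for-like pair that shows how much of a late result depends on who still has data. Dropping half of that pair after Week 12 without declaring it would leave a listed secondary endpoint only partly reported at the two durability time points.

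**Working it through.** **1. Can the sentences be reconciled?** One reading would apply the Week 12 limit to the plot only. The wording does not allow this, because the limited sentence covers summaries as well as plots, and the next sentence contrasts it with M=E summaries at each visit. As written, the summary is limited too.

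**2. Visits affected.** SAP Table 3-1 has post-baseline HIV-1 RNA windows at Weeks 4, 8, 12, 16, 24, 36 and 48, which is 7 visits.

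- M=F through Week 12 covers Weeks 4, 8 and 12, so 7 − 3 = 4 visits are dropped: Weeks 16, 24, 36 and 48.
- Snapshot (SAP 6.2.2.3) is planned at Weeks 12, 24 and 48. It covers 2 of the 4 and includes a non-success category for "Missing data during the window but on study drug".
- That leaves 4 − 2 = 2 visits, Weeks 16 and 36, where M=E would be the only planned proportion below 50 copies/mL and no missing row would appear.

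**3. How far the two methods can diverge.** The documents give no expected missing-data rate, so this is an illustration. The assumptions are FAS = 64 (the reduced sample size in SAP 1.3), no observed value of 50 or more, and d subjects missing at the visit.

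- M=F = (64 − d)/64
- M=E = (64 − d)/(64 − d) = 100% for every d
- Intervals are exact (Clopper-Pearson) two-sided 95%, the method SAP 6.2.2.5 specifies.

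| d missing | M=F | M=F exact 95% CI | M=E | M=E lower limit |
|---|---|---|---|---|
| 0 | 64/64 = 100% | 94.4 to 100 | 100% | 94.4 |
| 1 | 63/64 = 98.4% | 91.6 to 100.0 | 100% | 94.3 |
| 2 | 62/64 = 96.9% | 89.2 to 99.6 | 100% | 94.2 |
| 3 | 61/64 = 95.3% | 86.9 to 99.0 | 100% | 94.1 |
| 4 | 60/64 = 93.8% | 84.8 to 98.3 | 100% | 94.0 |
| 5 | 59/64 = 92.2% | 82.7 to 97.4 | 100% | 93.9 |

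The range 0 to 5 is a rough guide. In the two earlier switch studies described in protocol 1.2.3, 97% and 92% were suppressed at Week 48 after switching to E/C/F/TAF, so 3% to 8% were not: 0.03 × 64 = 1.9 and 0.08 × 64 = 5.1. Those percentages mix viraemia with missing data, so they do not estimate d.

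**4. What the plan's precision figures show.** SAP 1.3 states half-widths of ±5.9% (90%, n = 100) and ±5.3% (95%, n = 64). The formula 1.96 × √(p(1 − p)/n) gives 5.88% and 5.34%, so both reproduce. Neither depends on this point, and correcting it changes no design figure.

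**The case against.** The strongest objection is that no information is lost. The two methods share a numerator, the number of observed values below 50. M=E is tabulated at every visit with counts, and the FAS size is reported, so M=F is the M=E count divided by FAS N, and the number missing is FAS N minus the M=E denominator. This is correct, and it makes the loss one of presentation. A reader could rebuild the point estimate and the interval, but a listed endpoint should be reported without requiring that.

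Second, snapshot remains at Weeks 24 and 48, and the visits it does not cover, Weeks 16 and 36, carry no response endpoint. Under the illustration, snapshot would show the same figures as M=F if the same subjects lack data. SAP 6.1.1.2 also cross-classifies virologic failure with drug discontinuation by Week 48. This stands and limits the consequence. Snapshot is still a different analysis: it uses on-treatment data only, SAP 6.2.2.5 states no such limit for M=F, and the protocol asks subjects who stop drug to keep attending visits.

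Third, protocol support is looser than the synopsis alone suggests. In protocol 8.4.2 the weeks attach to snapshot, both protocol passages name M=F only as an example, and M=F is not in the protocol's secondary endpoint list. This also stands. The firmest conflict is therefore inside the SAP, between 6.2.2.5 and 6.2.1, and it does not need the protocol.

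Fourth, the FAS may be smaller than 64, because SAP 3.1.2 excludes subjects whose baseline regimen included Stribild or Descovy. This shifts the illustration slightly and does not affect the contradiction.

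**Conclusion.** The concern holds. SAP 6.2.2.5 contradicts itself on the M=F visits. Its restrictive sentence conflicts with SAP 6.2.1 and the protocol synopsis, and SAP 6.3 does not record the change. If the restrictive sentence is followed, M=F is missing at 4 of 7 post-baseline visits, including the two durability time points.

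The consequence is moderate. The Week 12 primary endpoint is untouched, no hypothesis is tested, snapshot still penalises missing data at Weeks 24 and 48, and M=F can be derived from the M=E counts. Under the assumptions above, the two methods agree when nobody is missing and differ by 100 − 92.2 = 7.8 percentage points with 5 of 64 missing. The contradiction should be corrected before the analysis is programmed.

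**What to change.** In the M=F sentence of SAP 6.2.2.5, change Week 12 to Week 48, so that both methods are summarised at every visit with the exact intervals already specified there.

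If the Week 12 limit is intended, three edits are needed instead: restrict M=F to Week 12 in SAP 6.2.1, correct the general each-visit sentence in SAP 6.2.2.5, and record the departure from the protocol, with its reason, in SAP 6.3.

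The first option costs one phrase and four more visits through an M=F program that is already planned. HIV-1 RNA windows already run to Week 48, so no new data are needed.

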#### 6.2.2.6. Analysis of CD4+ cell count

Analysis of CD4+ cell count will be based on on-treatment data (ie, data collected up to 1 day after the last dose date of study drug) using observed data (ie, missing will be excluded) for subjects in the FAS.

The change from baseline in CD4+ cell count at Weeks 12, 24, and 48 will be summarized overall and by Parts 1 and 2 using descriptive statistics. The change from baseline in CD4+ cell count will be similarly summarized at the visits other than Weeks 12, 24, and 48.

#### 6.2.2.7. Analysis of CD4%

Analysis of CD4% will be based on on-treatment data (ie, up to 1 day after the last dose date of study drug) using observed data (ie, missing will be excluded) for subjects in the FAS.

The change from baseline in CD4% at Weeks 12, 24, and 48 will be summarized overall and by Parts 1 and 2 using descriptive statistics. The change from baseline in CD4% will be similarly summarized at the visits other than Weeks 12, 24, and 48.

### 6.3. Changes From Protocol-Specified Efficacy Analyses

For the primary efficacy endpoint, PVR at Week 12, the protocol specifies that 95% CIs will be generated using the normal approximation method, but in the SAP, both the normal approximation and the exact methods are specified.

## **7. SAFETY ANALYSES**

Safety data will be summarized for the subjects in the Safety Analysis Set. All safety data collected on or after the date of the first dose of study drug up to the last dose date of study drug plus 30 days for subjects who have permanently discontinued study drug, or all available data for subjects who are ongoing will be summarized overall and by Parts 1 and 2, unless specified otherwise. All safety data will be included in data listings.

### **7.1. Adverse Events and Deaths**

#### **7.1.1. Adverse Event Dictionary**

Adverse events will be coded using the Medical Dictionary for Regulatory Activities (MedDRA, latest version). System organ class (SOC), high level group term (HLGT), high level term (HLT), preferred term (PT), and lower level term (LLT) will be attached to the clinical database.

#### **7.1.2. Adverse Event Severity**

AEs are graded by the investigator as Grade 1 (mild), Grade 2 (moderate), Grade 3 (severe) or Grade 4 (life threatening) according to toxicity criteria specified in the Study Protocol Appendix 4. The severity grade of events for which the investigator did not record severity will be categorized as “missing” for tabular summaries and data listings, and will be considered the least severe for the purposes of sorting for data presentation.

